### 8.1.1 Information to be collected on screening failures

Patients who sign an ICF and subsequently found to be ineligible prior to randomization will be considered a Screen Failure. All reasons for a Screen Failure should be recorded on the appropriate CRF. The demographic information, informed consent, and Inclusion/Exclusion pages must also be completed for Screen Failure patients. No other data will be entered into the clinical database for patients who are Screen Failures, unless the patient experienced a SAE during the Screening Phase (see Section 10.1.3 for SAE reporting details). If the patient fails to be randomized, the IRT must be notified within 2 days of the Screen Fail that the patient was not randomized.

Patients who are randomized and fail to start treatment will be considered an early terminator. The reason for early termination should be recorded on the appropriate CRF.

Patients randomized in error (= mis-randomized subjects) are defined as those subjects who were mistakenly randomized into the IRT prior to the site confirming all eligibility criteria had been met and to whom no study medication was given. Mis-randomized subjects will be treated as Screen Failures.

## 8.2 Patient demographics/other baseline characteristics

Baseline assessments will occur during the Screening Visit or the Baseline Visit depending on the assessment as indicated in Table 8-1.

Patient demographics and Baseline characteristics to be collected for all patients include: year of birth, age, sex, race, ethnicity, height (cm), weight (kg). Patient race and ethnicity data are collected and analyzed to identify any variations in safety or efficacy due to these factors as well as to assess the diversity of the study population as required by Health Authorities.

### 8.2.1 Smoking history

The current and/or previous use of tobacco products will be recorded, as well as the estimated number of pack-years based on the approximate consumption per year. Non-smokers will be

advised not to start smoking during the study. Patients will be stratified according to current smoking status (up to 20% smokers per arm) since smoking has a well-known impact on treatment efficacy in TED.

### 8.2.2 Tuberculosis screening

A central laboratory immunological test (QuantiFERON TB-Plus) must be performed at Screening to screen the patient population for latent tuberculosis infection. The results must be known prior to randomization to determine the patient's eligibility for the study.

Patients with a positive test may participate in the study if further work up (according to local practice/guidelines) establishes conclusively that:

- The patient has no evidence of active tuberculosis.
- If presence of latent tuberculosis is established then treatment must have been initiated and maintained according to local guidelines prior to randomization.

The QuantiFERON TB-Plus test will be analyzed by the central laboratory. Details on the collection, processing and shipment of samples and reporting of results by the central laboratory are provided in the laboratory manual.

### 8.2.3 Relevant medical history/ current medical history

Relevant medical history and current medical conditions, not including TED, prior to signing the ICF will be recorded in the Medical History eCRF page. Whenever possible, diagnoses and not symptoms will be recorded.

### 8.2.4 Prior and concomitant medications

Concomitant medications and prior medications taken over the 6 months preceding study enrollment for reasons other than thyroid disease and TED will be captured at the Screening Visit, and updated as necessary in the relevant eCRF.

### 8.2.5 TED and thyroid medical and treatment history

Disease history will be collected at Screening. The information to be collected and entered in the TED History eCRF page and Prior TED Therapies eCRF page will include the following:

- Date of onset of TED symptoms.
- Date of first diagnosis of TED.
- Underlying thyroid condition (Graves' disease, Hashimoto's thyroiditis, other).
- Previous treatments for TED (including but not limited to previous use of biologic therapies) and the reason for discontinuation of each therapy.

### 8.2.6 Serum pregnancy test

A serum pregnancy test will be performed for females of childbearing potential at Screening.

### 8.2.7 Other baseline characteristics

Other Baseline characteristics will be collected as described in Section 8.3, Section 8.4 and Section 8.5.

# 8.3 Efficacy

Efficacy assessments will be performed for both eyes at each assessment time point. The most severely affected eye will be defined as the "study eye" at the Baseline Visit. If there is a discrepancy between CAS and proptosis in determining the study eye, this will be adjudicated always to the eye with the most significant proptosis. In case both eyes show a similar degree of proptosis, other inflammatory signs and symptoms (CAS) should be taken into account by the investigator for the selection of the study eye. If both eyes are affected equally, the Investigator will choose the "study eye". Both eyes will be assessed for efficacy but the study eye will be used to assess the primary, secondary **CAS** outcome measures.

In the event of a major healthcare disruption (e.g., a pandemic or epidemic) that limits or prevents on-site study visits, selected efficacy assessments (if feasible for the individual assessments) can alternatively be done via phone calls/virtual contacts or visits of site staff to the patient's home, depending on local regulations and capabilities. Special efforts should be made to conduct the Week 16, R16 and NR16 visits on site, if feasible. If it is not feasible to conduct these visits on-site, visits to the patient's home or a virtual visit if a home visit not feasible, should be attempted.

## 8.3.1 Clinical activity score according to EUGOGO

TED activity will be assessed using the CAS at the frequency indicated in the study schedule (Table 8-1 and Table 8-2) based on the following signs and symptoms in accordance with the European Group on Graves' Orbitopathy (EUGOGO) guideline (Mourits et al 1997, Bartalena et al 2016):

- Symptoms
  - Spontaneous retrobulbar pain
  - Pain on attempted upward or downward gaze
- Signs
  - Redness of eyelids
  - Redness of conjunctiva
  - Swelling of caruncle or plica
  - Swelling of eyelids
  - Swelling of conjunctiva (chemosis)

For each item present, 1 point is given. The sum of these points is the CAS score (Mourits et al 1997), i.e., minimum score of 0 and maximum score of 7.

- Inactive TED = CAS < 3.
- Active TED =  $CAS \ge 3$ .

## 8.3.2 Proptosis

Proptosis measurements will be performed (ideally by the same observer) at the frequency indicated in the study schedule (Table 8-1 and Table 8-2). The same Hertel instrument, and the same outer intercanthal distance, should be used for each measurement. Instructions for the measurement of proptosis are included in ophthalmological manual (proptosis [exophthalmometry] assessment).

### 8.3.3 Diplopia grading

Diplopia will be graded according to the Gorman score/subjective diplopia score (Bahn et al 1987). This assessment, which is also called "Bahn-Gorman Score" comprises 4 different grades:

- 0 = No diplopia
- 1 = Intermittent diplopia (i.e., diplopia in primary position of gaze when tired or when first awakening)
- 2 = Inconstant diplopia
- 3 = Constant diplopia

A change of one grade will be considered to be clinically relevant.

### 8.3.4 **Ophthalmological assessments**

Ophthalmological assessments will be performed as indicated in a separate ophthalmological manual. These examinations should include subjective symptoms (e.g., epiphora, photophobia), Worth test, ocular motility (measured in degrees, by means of the Light Reflex Method [Dolman et al 2012]), best corrected visual acuity (Snellen), visual field tests, pupil examination, swinging flashlight test, color vision assessment (Ishihara color plates), lid retraction, intraocular pressure (Goldman), fluorescein staining of the cornea, slit lamp examination, spectral domain-optical coherence tomography (SD-OCT) assessment of the macula and papilla and optic nerve assessment (only nonmydriatic). If significant abnormalities are noted compared to previous visits, including a loss of two lines or more of vision, development of pupil abnormalities including afference pupillary defect, rise in intraocular pressure, development of corneal infiltrates, or other abnormalities not here specified but of concern to the ophthalmologist, further investigations of visual function will be conducted according to the ophthalmologist decision.

### 8.3.5 Disease severity assessments

Disease severity will be assess according to EUGOGO guidelines (Bartalena et al 2016).

Severity	Parameters
Mild TED	Patients whose features of GO have only a minor impact on daily life insufficient to justify immunosuppressive or surgical treatment. They usually have one or more of the following: minor lid retraction (< 2 mm), mild soft-tissue involvement, exophthalmos < 3 mm above normal, no or intermittent diplopia and corneal exposure responsive to lubricants.
Moderate to severe TED	Patients without sight-threatening GO whose eye disease has sufficient impact on daily life to justify the risks of immunosuppression (if active) or surgical intervention (if inactive). They usually have 2 or more of the following: lid retraction $\geq 2$ mm, moderate or severe soft-tissue involvement, or exophthalmos $\geq 3$ mm above normal, inconstant or constant diplopia.
Sight- threatening TED	Patients with DON and/or corneal breakdown

To assess disease severity, the following parameters will be examined (refer to ophthalmological manual):

Parameter	Assessments	
Lid retraction	Distance between the lid margins in mm with the patient looking in the primary position, sitting relaxed and with distant fixation	
Soft-tissue involvement	Eyelid swelling, redness of eyelids (erythema), conjunctival redness or conjunctival edema/swelling (chemosis)	
Exophthalmos	Measured in mm using the same Hertel exophthalmometer and same outer intercanthal distance for an individual patient.	
Diplopia	Subjective diplopia score	
Corneal exposure	Normal/staining/erosion/ulceration	
Optic nerve involvement	Best corrected visual acuity	
	Color vision	
	Visual fields	
	Optic disc (OCT assessment)	
	
 
Relative afferent pupillary defect (absent/present, assessed by swinging flashlight test)
 
	

### 8.3.6 Thyroid eye disease quality of life

Please refer to Section 8.5.1.

### 8.3.7 Appropriateness of efficacy assessments

The efficacy assessments selected are considered appropriate for this study in patients with moderate to severe TED.

### 8.4 Safety

Safety assessments are specified below with the assessment schedule detailing when each assessment is to be performed. For details on AE collection and reporting, refer to AE section (Section 10).

Assessment	Specification
Physical examination	A complete physical examination will include the examination of general appearance, skin, neck (including thyroid), eyes, ears, nose, throat, lungs, heart, abdomen, back, lymph nodes, extremities, vascular, and neurological. If indicated based on medical history and/or symptoms, rectal, external genitalia, breast, and pelvic examinations will be performed.
	Information for all physical examinations must be included in the source documentation at the study site. Clinically relevant findings that are present prior to signing informed consent must be recorded on the appropriate CRF that captures medical history. Significant findings made after signing informed consent which meet the definition of an AE must be recorded as an AE.
Vital signs	Vital signs include systolic blood pressure (SBP), diastolic blood pressure (DBP), and pulse measurements. After the patient has been sitting for 5

Assessment	Specification
	minutes, with back supported and both feet placed on the floor, SBP and DBP will be measured 3 times using an automated validated device with an appropriately sized cuff. The repeat sitting measurements will be made at 1 to 2 minute intervals and the mean of the 3 measurements will be used. The results of all measurements, including the mean measurement, should be recorded in the source data.
	If possible, assessments should be performed by the same study site staff member and at the same arm throughout the study.
	Normal blood pressure will be defined as SBP of 90 to < 120 mmHg, and diastolic blood pressure of 60 to < 80 mmHg under the measurement conditions outlined above. Notable blood pressure findings will be hypertension (SBP of $\geq$ 140 mmHg and/or DBP of $\geq$ 90 mmHg) or hypotension (SBP of < 90 mmHg and/or a DBP of < 60 mmHg). A blood pressure indicative of prehypertension (SBP of 120 to < 140 mmHg and/or DBP of 80 to < 90 mmHg) will not be regarded as notable (Whelton et al 2017).
	A normal pulse rate will be defined as a rate of 60 to 100 beats per minute (bpm) under the measurement conditions outlined above. Notable pulse rate will be a rate below 60 bpm (bradycardia) or above 100 bpm (tachycardia).
	Whether action needs to be taken to address notable vital signs will be decided by the Investigator, taking into account the overall status of the patient. No specific action is foreseen as part of the study protocol.
Height and weight	Height in centimeters (cm) and body weight (to the nearest 0.1 kilogram (kg) in indoor clothing, but without shoes) will be measured.

In the event of a major healthcare disruption (e.g., a pandemic or epidemic) that limits or prevents on-site visits to the study site, regular phone calls, virtual contacts or visits of site staff to the patient's home, depending on local regulations and capabilities, will occur (according to the visit schedule or weekly if during the weekly induction phase) for safety monitoring and review of the patient's ophthalmological and general health status until the patient can again visit the site. This is necessary to ensure that there are no safety concerns to the patient requiring treatment interruption or discontinuation. If in the opinion of the investigator the patient requires an in-person assessment, arrangements will be made for the patient to be evaluated at the site, or if this is not feasible, by a local ophthalmologist or in an emergency healthcare setting. In consultation with the investigator, selected ophthalmological assessments (e.g., visual acuity, intraocular pressure, color vision) can also be done by a local optometrist to enable continuous monitoring of the patient's ophthalmological status if on-site visits or visits to a local ophthalmologist are not feasible. Assessment results have to be reported to and discussed with the investigator as soon as possible in this case.

Events qualifying for being reported in the case report form (e.g., AEs) should be entered as appropriate.

If patients cannot visit the site to have urine pregnancy tests done, urine pregnancy test kits may be shipped or provided directly to the patient (e.g., together with the study drug). After appropriate instruction, patients can perform the urine pregnancy test at home and report the result to the site. It is important that patients do the pregnancy test first and only if the test result is negative proceed with the administration of the study drug. Depending on local regulations and capabilities, study site staff may visit the patient at home to draw blood/urine samples if needed.

### 8.4.1 Laboratory evaluations

Clinically notable laboratory findings are defined in Appendix 1. Please refer to Table 8-1 and Table 8-2 for the timing of laboratory evaluations.

Clinically significant abnormalities must be recorded as either medical history/current medical conditions or AEs as appropriate.

Test category	Test name
Hematology	Hematocrit, Hemoglobin, Platelets, Red Blood Cells (RBCs), White Blood Cells (WBCs), Differential (Basophils, Eosinophils, Lymphocytes, Monocytes, Neutrophils, Bands)
Chemistry	Albumin, Alkaline Phosphatase, Alanine Amino Transferase (ALT), Aspartate Amino Transferase (AST), Gamma-glutamyl Transferase (GGT), Lactate Dehydrogenase (LDH), Bicarbonate, Calcium, Magnesium, Phosphorus, Chloride, Sodium, Potassium, Creatinine, Direct Bilirubin, Indirect Bilirubin, Total Bilirubin, Total Cholesterol, Low Density Lipoprotein (LDL), High Density Lipoprotein (HDL), Total Protein, Triglycerides, Blood Urea Nitrogen (BUN) or Urea, Uric Acid, Glycated Hemoglobin (HbA1c) will be assessed from fasting blood samples.
Urinalysis	The central laboratory will provide dipsticks to the sites for local analysis of urine. Dipstick analysis will measure specific gravity, protein, glucose and blood. Microscopy and white blood cell count and red blood cell count sediments will be assessed in case of an abnormal dipstick test. Only samples with abnormal dipstick will be assessed by the central laboratory.
	Study sites should record the results in the source documentation.
Pregnancy test	Please refer to Section 8.4.2.
Fertility test	A follicle stimulating hormone (FSH) test will be performed if required for fertility testing in the absence of other records of fertility (see Section 8.4.2)

### 8.4.2 Pregnancy and assessments of fertility

### Pregnancy testing

Secukinumab must not be given to pregnant women; therefore, effective methods of birth control must be used for women of childbearing potential (see Exclusion Criteria definitions, Section 5.2).

A serum  $\beta$ -human chorionic gonadotropin (hCG) test will be performed in all women of childbearing potential at Screening. All pre-menopausal women who are not surgically sterile at Screening will have local urine pregnancy tests performed as indicated in Table 8-1 and Table 8-2. A positive urine pregnancy test requires immediate interruption of study treatment until serum  $\beta$ -hCG is performed and found to be negative. If positive, the patient must be discontinued from the trial. Additional pregnancy testing might be performed if requested per local requirements. Refer to Section 10.1.4 for details on reporting of pregnancy.

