# 9 Study discontinuation and completion

# 9.1 Discontinuation and completion

# 9.1.1 Study treatment discontinuation and study discontinuation

The investigator closely monitors the disease activity of a patient throughout the entire study and must discontinue study treatment or study participation for a given patient if he/she believes that continuation would negatively impact the patient's well-being.

Discontinuation of study treatment for a patient occurs when study treatment is stopped earlier than the protocol planned duration and can be initiated by either the patient or the investigator.

Study treatment must be discontinued under the following circumstances:

- Subject decision.
- If any of the following (evidence of disease progression) occurs in the study eye or fellow (contralateral) eye:
  - Compressive optic neuropathy that in the opinion of the investigator requires urgent surgical intervention or medical treatment with glucocorticoids
  - Severe corneal injury that requires surgical treatment
  - Severe/major loss of vision defined as a decrease of best-corrected visual acuity to below 0.1 (Snellen equivalent of 20/200)
  - Other abnormalities not here specified but that the investigator determines would require study treatment discontinuation
- Emergence of the following AEs:
  - Any severe or SAE that is not compatible with administration of study medication, including AEs that require treatment with an unacceptable concomitant medication.

- Onset of lymphoproliferative disease or any malignancy, except for treated basal cell carcinoma, treated actinic keratoses, treated *in situ* carcinoma of the cervix or non--invasive malignant colon polyps which are being or have been removed.
- Life-threatening infection.
- Severe hypersensitivity reaction or anaphylactic reaction.
- Any laboratory abnormalities that in the judgment of the investigator are clinically significant and are deemed to place the patient at a safety risk for continuation in the study (a general guidance on clinically notable laboratory values is provided in Appendix 1).
- Pregnancy.
- Use of any biologic immunomodulating agent except secukinumab.
- Other treatment or procedure for TED in case of worsening of the disease.
- Any protocol deviation that results in a significant risk to the patient's safety.

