- Use of prohibited treatment as per recommendations in the prohibited treatment section if the treatment with prohibited medication increases the patient's safety risk and if it cannot be discontinued.
- Emergency unblinding

If discontinuation of study treatment occurs, the investigator should make a reasonable effort to understand the primary reason for the patient's premature discontinuation of study treatment and record this information.

In addition to the study treatment discontinuation criteria above, which apply throughout the entire study, the following criterion applies from week 16 onwards for discontinuation of study participation of a patient:

Any deterioration compared to baseline values that the investigator considers to be clinically relevant in this individual case will result in study discontinuation of the patient. The evaluation should take into account the overall course of the disease of the individual case (e.g., individual fluctuations of ocular parameters).

Patients may decide to discontinue their participation in the study for any reason at any time.

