### Premature discontinuation of study treatment

Patients who prematurely discontinue study treatment during the double-blind treatment period (Weeks 0 - 16) or during a course of open-label secukinumab administered during the followup period (at or after Week 16), for any reason other than withdrawal of informed consent should **not** be considered as discontinued from the study. **Where possible, they should return for the study visits indicated** in the Assessment Schedule during treatment. These include up to Week 16 (if discontinued during double-blind treatment), up to NR32 (for non-responders), and up to R16 (for relapsers). In case patients are not willing to continue attending further study visits, they should attend an End of Treatment (EOT) visit 4 weeks after the last dose of study drug. This EOT visit includes all assessments of the Week 16 (if discontinued during doubleblind treatment), NR32 (for non-responders) or R16 (for relapsers) visit. Additionally, a follow-up visit (EOS) should be done 12 weeks after last study drug administration, including all assessments done at: Week 24 (if discontinued during double-blind treatment), Week NR40 (for non-responders) or Week R24 (for relapsers).

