### Premature discontinuation of study

Participants who prematurely discontinue the study for any reason should be scheduled for a visit as soon as possible, at which time all of the assessments listed for the study discontinuation visit will be performed. This study discontinuation visit should include all assessments of the Week 16 (if discontinued during double-blind treatment), NR32 (for non-responders), R16 (for relapsers) or Week 68 (for patients who discontinued during the follow-up period) visit.

Additionally, all randomized and/or treated patients should have a follow-up (EOS) visit conducted 12 weeks after last administration of study treatment, if not yet completed (or at least a safety follow-up call or contact, if a visit cannot be performed). This EOS visit includes all assessments of the Week 24 (if discontinued during the double-blind treatment period or the follow-up for responders), Week NR40 (for non-responders) or Week R24 (for relapsers) visit. The information collected is recorded in the eCRF. Documentation of attempts to contact the patient should be recorded in the source documentation.

For all premature discontinuations noted above, if the patient fails to return for these assessments for unknown reasons, every effort (e.g., telephone, e-mail, letter) should be made to contact the participant/pre-designated contact as specified in the lost to follow-up section. This contact should preferably be done according to the study visit schedule.

If the patient cannot or is unwilling to attend any visit(s), the site staff should maintain regular telephone contact with the patient, or with a person pre-designated by the patient. This telephone contact should preferably be done according to the study visit schedule.

After study treatment discontinuation or study discontinuation, at a minimum, in abbreviated visits, the following data should be collected at clinic visits or via telephone/email contact:

- New/concomitant treatments
- AEs/SAEs

The investigator must also contact the IRT to register the patient's discontinuation from study treatment.

If discontinuation occurs because treatment code has been broken, please refer to Emergency breaking of treatment code section.

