#### 10.1.4 Pregnancy reporting

If a female trial patient becomes pregnant, the study treatment should be stopped, and the trial patient must be asked to read and sign pregnancy consent form to allow the Study Doctor ask about her pregnancy.

To ensure patient safety, each pregnancy occurring after signing the informed consent must be reported to Novartis within 24 hours of learning of its occurrence. The pregnancy should be followed up to determine outcome, including spontaneous or voluntary termination, details of the birth, and the presence or absence of any birth defects, congenital abnormalities, or maternal and/or newborn complications.

Pregnancy should be recorded and reported by the investigator to the Novartis CMO&PS. Pregnancy follow-up should be recorded on the same form and should include an assessment of the possible relationship to the study treatment of any pregnancy outcome. Any SAE experienced during pregnancy must be reported.

Pregnancy outcomes should be collected for the female partners of any males who took study treatment in this study. Consent to report information regarding these pregnancy outcomes should be obtained from the mother.

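### Within a treatment course, Protocol 8.4.2 takes a patient with a confirmed pregnancy out of the trial while 9.1.1 keeps her in; for a pregnancy found at Week 12 this can lose the Week 16 status

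*Protocol*

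**What the plan says.** Protocol 8.4.2 (Pregnancy testing) interrupts study treatment after a positive urine test until a serum test is done. For the serum test it then says: "If positive, the patient must be discontinued from the trial".

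Protocol 9.1.1 puts pregnancy in a list introduced by "Study treatment must be discontinued under the following circumstances". Under its paragraph on premature discontinuation of study treatment, patients who stop during Weeks 0 to 16 or during an open-label course "for any reason other than withdrawal of informed consent should" not count as having left the study. Where possible they return for visits up to Week 16, NR32 or R16. Study exit is handled separately: "the following criterion applies from week 16 onwards for discontinuation of study participation of a patient", and that criterion is clinically relevant deterioration, not pregnancy.

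A patient who does leave the study gets one visit as soon as possible, with the Week 16, NR32 or R16 assessments if she leaves during a course. In addition, "all randomized and/or treated patients should have a follow-up (EOS) visit conducted 12 weeks after last administration of study treatment".

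Protocol 10.1.4 says: "If a female trial patient becomes pregnant, the study treatment should be stopped". It is silent on study participation.

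**The concern.** The two instructions lead to different visit schedules for the same event. The protocol's glossary separates stopping study treatment from withdrawing from the study, and 8.4.2 itself moves from interrupting treatment (urine test) to leaving the trial (serum test). A site could therefore fairly read 8.4.2 literally.

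What is at stake is mainly the Week 16 status. Both primary estimands in Protocol 2.1 ignore treatment discontinuation and use the response status obtained afterwards, so a patient who stops treatment because of pregnancy should still be assessed at Week 16. If she is taken out of the trial, that assessment may not happen. The non-responder rule in Protocol 12.4.4 is written for patients who do not discontinue the trial, so it would not clearly cover her. SAP 2.5.3 replaces no missing values, and SAP 2.1 generally leaves them out of percentages.

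**Working it through.** **Inputs.** Dosing days are 1, 8, 15, 22, 29, 57, 85 (double-blind) and 113, 120, 127, 134, 141, 169, 197 (open-label, non-responders). Urine tests come from Tables 8-1 and 8-2. A non-responder who takes open-label treatment has 10 after baseline: Weeks 4, 8, 12, 16, NR20, NR24, NR28, NR32, NR40, NR56. Protocol 6.7.2 places dosing after the visit assessments, so a positive test means that day's dose is withheld and the last dose is the previous one.

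**The plan's windows, reproduced.** SAP 2.1.1.2 gives the upper limit as the integer part of (target day + next target day)/2.
- Week 12 upper limit: (85 + 113)/2 = 99, so Week 16 starts on day 100.
- Week 16 upper limit: (113 + 141)/2 = 127.
- NR28 upper limit: (197 + 225)/2 = 211, so NR32 starts on day 212.
- NR32 upper limit: (225 + 281)/2 = 253.

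All agree with SAP Tables 2-1 and 2-2.

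**Rule applied.** The end-of-study (EOS) day is the last dose day + 84. A visit is lost if the 9.1.1 paragraph keeps it and the EOS visit does not fall in its window.

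| Positive test (day) | Last dose | EOS day | EOS maps to | Lost under 8.4.2 |
|---|---|---|---|---|
| Week 4 (29) | 22 | 106 | Week 16 | Weeks 8, 12 |
| Week 8 (57) | 29 | 113 | Week 16 | Week 12 |
| Week 12 (85) | 57 | 141 | past Week 16 | Week 16 |
| Week 16 (113) | 85 | 169 | same day under both rules | none |
| NR20 (141) | 134 | 218 | NR32 | NR24, NR28 |
| NR24 (169) | 141 | 225 | NR32 | NR28 |
| NR28 (197) | 169 | 253 | NR32, last day | none |
| NR32 (225) | 197 | 281 | NR40 | none: visits are kept only up to NR32 |
| NR40, NR56 | 197 | – | – | none: after the course |

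For the Week 16 row, the Section 3 visit for untreated non-responders is on day 113 + 56 = 169, the same day as 85 + 84.

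The loss is therefore 1 or 2 visits at 5 of the 10 tests.

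**The Week 12 case.** Day 141 is 14 days past day 127. This does not depend on exact visit days: a Week 8 dose anywhere in its window (days 44 to 71) puts an EOS visit held exactly 84 days later on days 128 to 155. The discontinuation visit would have to wait at least 100 − 85 = 15 days to count as Week 16; held promptly, it maps to Week 12 (days 72 to 99). Under 9.1.1 the day 113 visit stays on the schedule.

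**Credit for the discontinuation visit.** If it is held separately from the test visit, it offsets one lost visit. The net loss is then 2 − 1 = 1 at Week 4 and NR20, and 1 − 1 = 0 at Weeks 8, 12 and NR24. At Week 12 the count nets to zero, but the Week 16 status is still missing unless that visit falls on day 100 or later.

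**The case against.** The strongest reply is that the loss is narrow. It needs a pregnancy first found at one particular visit. A full set of Week 16 assessments is still collected then, only mapped to Week 12, and 9.1.1 itself keeps the Week 16 visit only where possible. All of this stands and is why the point has low priority. It does not remove the contradiction.

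A reader might infer four stronger things that the documents do not support.

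- **That the conflict reaches every pregnancy test, including follow-up.** The 9.1.1 paragraph covers only stops during a treatment course and keeps visits only up to Week 16, NR32 or R16. When no treatment is ongoing, 8.4.2 is the only operative instruction. For the same reason, a loss of NR56 after a positive test at NR32 or NR40, or of responder follow-up visits, should not be counted.
- **That 10.1.4 is a second contradiction.** It is a reporting section. Stopping treatment is consistent with 9.1.1 but also compatible with leaving the trial.
- **That safety follow-up is lost.** The EOS visit applies on either route. "After study treatment discontinuation or study discontinuation, at a minimum, in abbreviated visits, the following data should be collected" is followed by new treatments and AEs/SAEs. Under 10.1.4 the pregnancy is followed to outcome, and "Any SAE experienced during pregnancy must be reported". The earlier SAE reporting cut-off in 10.1.3 for early study discontinuation would matter only for an unrelated SAE after the pregnancy had ended.
- **That the NR32 status is lost too.** On nominal days the EOS visit falls inside the NR32 window after a positive test at NR20, NR24 or NR28, though with no slack at NR28.

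**Conclusion.** The inconsistency is real and in current text, but confined to treatment courses. Following 8.4.2 instead of 9.1.1 costs 1 or 2 scheduled visits at 5 of 10 tests, gross of a separate discontinuation visit. It endangers the Week 16 status for one test only, Week 12.

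This rests on nominal visit days, the dose being withheld on the day of a positive test, and a prompt discontinuation visit. If the Week 8 dose were given despite a positive test that day, EOS would fall on day 57 + 84 = 141, and the Week 16 status would be at risk there as well.

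No sample size or alpha figure depends on the point. No pregnancy is documented. The amended SAP describes 28 randomized patients, omits superiority testing and reports no responders, so a lost status would alter a denominator rather than a test. The correction is worth making, mainly for any reuse of the protocol, but is not essential to this trial's results.

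**What to change.** In Protocol 8.4.2, replace removal from the trial with discontinuation from study treatment and follow-up as per Section 9.1.1.

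Do not add a permanent bar on later open-label treatment. Section 8.4.2 already says secukinumab must not be given to pregnant women. A further bar would be a new rule, and would shut out a patient whose pregnancy ended before a later relapse.

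The new wording also leaves patients tested outside a treatment course on their ordinary schedule. If the sponsor wants them to leave the trial, 8.4.2 should say so separately.

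The cost is one phrase and, for such a patient during a course, one or two already scheduled visits kept where possible. The contents list an MRI section (8.5.5) whose text is not visible, so whether any kept visit involves imaging unsuitable in pregnancy could not be checked.

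SAP 2.3.1 already displays the primary reason for premature discontinuation, so the study report needs at most a note of which rule the site applied, should a pregnancy have occurred.
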